The touch screen and content refinement work associated with Aim 1 will be conducted by [name] Agents Group at the College of Computer and Information Science at Northeastern University. [name] will oversee touch screen and content refinement. Once refinements are completed, beta testing will be conducted with Veterans at Bedford VAMC.

b. Clinical Trial Procedures

Clinical Trial Overview (Palo Alto, Boston, Hines, Iowa City):

Our setting is the inpatient services of four VA medical centers, Palo Alto, Boston, Hines, and Iowa City VA. Analyses will be done at Bedford ENRM VA Hospital and Hines VAMC.

Patients will receive standard medical care as expected.

If they decide to participate in this research study, they will be randomized to receive one of two interventions to support their transition back to home. Patients will be asked to complete a baseline survey about demographics and pre-discharge experience. Patients will receive a short education on care transitions (either a PowerPoint for control or on-screen Annie intervention training on the procedures).

Inpatient: During the inpatient stay, Annie will appear on a computer touch screen and will educate Veterans with CHF or COPD about the important components of a care transition as well as how to send and receive text messages on their mobile phone. Outpatient: Following discharge to home, Annie will continue to coach Veterans and improve post-discharge access to care through two-way computer-tailored text messaging made possible by VHA's new HealtheDialog system. The goals of the text messages are to remind Veterans of care transition pillars, assess whether Veterans have questions or are experiencing symptoms, provide assessment feedback, and to motivate Veterans to ask questions and share information with their primary care team. These are health coaching and motivational text messages. The control group will receive a maximum of four to six messages over the 30-day intervention period for the purpose of keeping them engaged in the study. All participants will be contacted 7 and 30 days after discharge to conduct follow-up assessments (surveys over the phone), each survey taking 30 minutes or less.

Recruitment and Participation for in-patient Veterans (Not at Bedford):

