4	Trial CHF Pre/Post Outcomes Questionnaire	At baseline and follow up, for patients with CHF of the testing
5	Trial COPD Pre/Post Outcomes Questionnaire	At baseline and follow up, for patients with COPD of the testing
6	Trial Outcomes Post Questionnaire	At follow-up of the testing for all participants
7	Trial Texting Usability Outcomes	Testing for the texting intervention component at follow up
8	Patient Semi-Structured Interview	At follow up of the testing for a small subset of participants
9	Caregiver Semi-Structured Interview and Background Questions	At follow up of the testing for a small subset of caregivers

We will begin our dissemination efforts when Aim 1 work is completed at the end of year 1 and then further expand our dissemination efforts in years 4 and 5 once implementation and clinical effectiveness data from the trial have been analyzed. Dissemination of lessons learned from implementation of Annie will begin in Year 3 and dissemination of trial evaluation outcomes will begin in year 5.

The following table lists our key data elements and data sources (see appendices):

Key Data Elements, and Data Sources (See Appendices for measures)	CDW Data	Patient Survey	Texting Accesses/data
Demographic characteristics	B	B, F	
Diagnoses/Comorbidities (CIRS-G)	B	B,F	
Rapid Estimate of Adult Literacy in Medicine (REALM) -Short Form		B	
Computer Attitudes Measure (CAM) and previous texting experience		B	
Patient-reported “red flags” (P4)		F	F
Patient access to Annie		F*	F
Care Transition Measure (CTM) (P1-4)		F	
Follow-up no-show rates (P3)	F	F	
Patient-provider communication		B,F	
Self-efficacy for managing chronic disease		B, F	
Health distress		B, F	
Self-report ratings of the relational agent		I*,F*	
1-month rehospitalization	F	F	
System Usability Scale (SUS)		I*,F*	
Technology Assessment Measure (TAM)		I*,F*	
Relational Agent Engagement Scale		I*	
Working Alliance Inventory (WAI) for collaborating with Relational Agent*		I*	
Preparedness for discharge		I,F	
User experience interviews		F**	
P (1,2,3,4) = Pillars of Care Transition Intervention Model; * intervention only, ** subset of intervention only, B= baseline, I= Immediate inpatient postintervention, and F = 1-month Follow-up			

List of data elements:

Data source	Data elements
CDW: Consult	Demographics, clinical diagnoses, procedures, and services
CDW: Inpatient	Demographics, clinical diagnoses, inpatient utilization

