3.5 Analysis Plan

For beta testing at VA Bedford:

We are the parent site to a multi-site clinical trial. We originally decided not to do any patient recruitment at Bedford, but to improve the pilot testing of our intervention components, we would like to add Bedford as a beta test site. In order to prepare our intervention components for pilot testing, we would like to beta test the components separately with a small group of patients at VA Bedford. We will gather feedback via surveys and semi-structured interviews on usability issues and suggestions for improvement so that we are better suited to move forward with pilot testing at VA Boston as well as the larger multi-site trial.

For all sites: Our procedures will consist of Corporate Data Warehouse administrative records, baseline data collection from participants, usage statistics of the HealtheDialog texting system, a follow-up participant call to assess outcomes, and Annie user experiences at the sites.

For Sub-Aim A (conducted at the Bedford VA): The independent variable will be randomized group assignment to the intervention (the Annie interface/content) or the control. Scores on the Care Transition Measure (CTM), a 15-item uni-dimensional measure of the quality of preparation for care transitions will be utilized. Randomization beta testing will be at the patient-level. We will compare the effectiveness of the pre-discharge component (e.g., not the post-discharge text messaging component) of the Annie intervention compared with control. The goal of this analysis will be to determine impact on quality of care transitions as indicated by CTM scores. Each of the 15 CTM items has a 4-point Likert response scale (strongly agree; agree; disagree; and strongly disagree) with the lowest possible score being 0 and the highest possible score being 100 and higher scores indicating a better quality care transition.

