All Aim 3 analyses will be done in partnership at ENRM VA and Hines VAMC. For Aim 3 effectiveness analyses, the independent variable will be group assignment (Annie or control) and all analyses will use an analyze-as-randomized intent-to-treat approach. In addition to measuring all rehospitalization, we will determine the relatedness of the rehospitalization to the index admission (relatedness defined as having COPD or CHF as a primary or secondary diagnosis on rehospitalization). Further we will assess the potential for prevention of the rehospitalization. There are several approaches to identifying potentially preventable rehospitalizations, including using software algorithms, and more rigorous manual chart/survey data reviews. We now propose to classify readmissions as possibly preventable using a gold standard review of all data from each patient. We will measure pre-post trend in urgent care utilization. For an 18-month period pre-index hospitalization and a six-to-twelve month period post-hospitalization (depending on time of

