We will rely on established measures and techniques to examine patient experiences of the Annie intervention. Patient factors known to moderate current technology use like age, education, income, vision correction, technology attitudes, and previous text messaging experience will be measured at baseline as part of demographic questionnaires and other established instruments. Research assistants will query all participants in-person in order to collect baseline responses before discharge. Pre-intervention measures will also include constructs related to the Care Transition Pillars such as patient-provider communication (information sharing), health distress, and self-efficacy for managing chronic disease (self-management ability and confidence) in order to be able to compare evaluation outcomes to baseline levels. Research assistants will call patients for the collection of post-intervention measures. As a quantitative measure of user preferences, intervention patients will also provide responses to validated questionnaires related to their experience with the virtual nurse coaching and texting technologies, including perceived usefulness and overall system usability. As a quantitative measure of performance, activity logs from the texting system will be examined to determine the number of text messages initiated by the system and received by participants. Intervention patients will also be asked whether an informal caregiver assisted with participation in the intervention. Finally, to gain more in-depth information regarding the experiences of patients and any challenges that they encountered during the outpatient automated texting intervention, a sub-sample of intervention participants will be interviewed (again via telephone) (n=25). Interviews will be audio recorded and transcribed for analysis. The phone interview portion will last up to 30-45 minutes. Participants who complete an interview will be mailed a \$10 incentive to thank them for their time. These interviews will be conducted by project staff at Bedford VAMC and Hines VAMC. Interview topics addressed with patient intervention participants are organized around the dimensions of the Socio-Technical Framework.

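### Preventability of readmissions is judged by a manual review of all patient data that can reveal the arm, with no masking of reviewers stated

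*Combined protocol and SAP*

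**What the plan says.** **Method.** Section 3.5 (Analysis Plan) describes the ways to identify preventable rehospitalizations, "including using software algorithms, and more rigorous manual chart/survey data reviews", and then proposes to "classify readmissions as possibly preventable using a gold standard review of all data from each patient". It gives no criteria for the classification and does not say who the reviewers are or what their file contains. The paragraph concerns the Aim 3 effectiveness analyses, in which randomized group is the independent variable.

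**Data held on each patient.**
- The all-sites paragraph of section 3.5 lists "usage statistics of the HealtheDialog texting system, a follow-up participant call to assess outcomes, and Annie user experiences" among the data.
- Later in section 3.5, "activity logs from the texting system will be examined to determine the number of text messages initiated by the system and received by participants".
- The key to the data-element table in section 3.4 (Data Collection) uses asterisks to mark items as "intervention only, subset of intervention only". The marked items include the relational-agent ratings, usability, technology assessment, engagement and working-alliance scales. User interviews are marked as a subset of the intervention arm.
- Section 3.4 also says that the tablet questionnaires contain questions flagged by arm.

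**Texting by arm.** In section 3.3 (Study Procedures), Annie patients get "two-way computer-tailored text messaging made possible by VHA's new HealtheDialog system", which includes symptom assessment and feedback. For the others, "The control group will receive a maximum of four to six messages over the 30-day intervention period", to keep them engaged in the study.

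**Masking.** Sections 3.4 and 4.2 state it for patients. Section 4.4 states it for the enrolling person until randomization. Section 4.6.1 gives study personnel access to data and codes, with no exception for outcome reviewers.

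**The concern.** Calling a readmission possibly preventable is a judgement. A reviewer who can see which material the patient received may judge the same clinical course differently in the two arms.

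A second problem does not depend on the reviewer's attitude. Annie patients are asked by text about symptoms, while control messages serve only to maintain engagement. An Annie file can therefore hold post-discharge symptom reports that a control file lacks, and an impartial reviewer would be judging on unequal evidence.

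If either happens, a difference between arms in preventable readmissions cannot be separated from the way the readmissions were classified. Of the rehospitalization measures in section 3.5, this is the one that rests on judgement.

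**Working it through.** The plan gives no event count, agreement figure or power for preventable readmissions, so there is no figure to reproduce. The check has two parts.

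**1. Would the file reveal the arm?**
- *Intervention-only scales.* Several are collected in hospital, right after the session and so before any readmission. They should be in most Annie files even if the 30-day call is missed, and in no control file.
- *Texting logs.* They can exist in both arms. They identify the arm by volume (at most four to six control messages in 30 days) and by content (two-way coaching against engagement messages).
- *Tablet questionnaires.* Both arms have them, with different questions.
- *User interviews.* Only 25 participants are interviewed, so these reveal little overall.
- *Masking of reviewers.* None is stated in the public text.

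A literal reading of all data therefore shows the arm for most patients.

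**2. How much could it matter? (illustration only)**

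Inputs from section 3.5: 300 patients per arm, and a readmission risk r of 12.7% to 21%, which the protocol labels annual. The window for the preventability review is not stated. Assumptions: one readmission per patient, a true preventable share q of 25% or 50% in both arms, and a shift s in the share called preventable in one arm.

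*Counts* at r = 20%, q = 25%: 300 × 0.20 = 60 readmitted per arm, and 60 × 0.25 = 15 preventable.
- Shift down by 5 or 10 points: 60 × 0.20 = 12 or 60 × 0.15 = 9. Ratios 12/15 = 0.80 and 9/15 = 0.60.
- Shift up by 5 or 10 points: 60 × 0.30 = 18 or 60 × 0.35 = 21. Ratios 18/15 = 1.20 and 21/15 = 1.40.

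*False-positive rate* of a two-sided 5% test of two proportions, n = 300 per arm, no true effect, downward shift in one arm:
- p1 = r × q, p2 = r × (q − s), d = p1 − p2, and p is the mean of p1 and p2
- SE0 = √(2p(1 − p)/n); SE1 = √((p1(1 − p1) + p2(1 − p2))/n)
- Rejection probability = Φ((d − 1.96·SE0)/SE1) + Φ((−d − 1.96·SE0)/SE1)

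Example, r = 20%, q = 25%, s = 10 points: p1 = 0.05, p2 = 0.03, d = 0.02, SE0 = 0.0160, SE1 = 0.01598. Then Φ(−0.711) + Φ(−3.21) = 0.239.

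| r | q | s = 0 | s = 5 points | s = 10 points |
|---|---|---|---|---|
| 12.7% | 25% | 0.050 | 0.075 | 0.167 |
| 12.7% | 50% | 0.050 | 0.062 | 0.103 |
| 20% | 25% | 0.050 | 0.091 | 0.239 |
| 20% | 50% | 0.050 | 0.070 | 0.137 |
| 21% | 25% | 0.050 | 0.093 | 0.249 |
| 21% | 50% | 0.050 | 0.071 | 0.142 |

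**The case against.** The strongest reply is that section 3.5 does not put texting logs, relational-agent scales or interviews into the review file. The sentence before contrasts software with manual review of charts and surveys, so all data may mean only a full chart and survey review. The logs are introduced elsewhere as a measure of performance, and the usability questionnaires as a measure of user preferences. On this view the plan leaves masking unspecified and does not mandate unmasking.

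Much of this stands. A reader might infer that the rule unmasks every reviewer. That needs the literal reading and is not established. A reader might also take texting records to exist only in the Annie arm. Section 3.3 contradicts this, because controls also receive messages. What does not fall away is that survey data are named, that some survey items exist in one arm only, and that no safeguard keeps them out of the file.

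The illustration is also open to challenge. The preventable share and the shift have no source in the documents. A 5-point shift leaves the error rate close to nominal. Counts of 12 v 15 and 9 v 15, each out of 60, would give p of about 0.51 and 0.17, so neither would be significant in a single trial. This is fair. The figures show that the outcome is sensitive to classification, not that a false finding is likely.

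**Conclusion.** The concern holds as a risk of bias in one additional outcome. The review described can show the arm to the person making the judgement and can give that person more evidence in one arm than in the other. The public text contains no masking step. The pages between section 5.0 and the reference list were not available for this review, so a statement there cannot be excluded.

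The size is unknown. Under the assumptions above, a 5-point shift gives a false-positive rate of about 6%-9%, and a 10-point shift about 10%-25%, against 5%.

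Two stronger conclusions are tempting and not supported:
- *That the bias favours Annie.* Reviewers might call coached patients' readmissions less preventable. Texted symptom reports or red flags could equally make a readmission look like a missed warning, and so more preventable. The documents do not settle the direction.
- *That the trial's main result is threatened.* The primary measure is a count of urgent care use, all rehospitalization is counted, and relatedness is defined by diagnosis. None of these uses the preventability judgement.

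**What to change.** Amend section 3.5 so that preventability is classified from a packet prepared by the data analyst:
- Include the index and readmission records, and only those data collected in the same form in both arms.
- Leave out texting logs, intervention-only survey items and user interviews.
- Redact mentions of the assigned material, including in the research note that section 4.5.2 places in the chart if that note names it.
- Reviewers classify without knowing the arm, and the analyst merges the arm after the classifications are complete.

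This deals with both problems, since reviewers no longer see the arm and both arms are judged on the same kind of evidence.

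The cost is analyst time for preparing packets and redacting free text from four sites. Texted red-flag information, which may bear on preventability, is also lost to the review. No extra reviewers or patients are needed. The change can be made after enrolment has ended, provided that it comes before the review.

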recruitment, we propose to extract data, our primary effectiveness measure (urgent care utilization) and dates. This is a pre-post difference in differences analysis, comparing the number of urgent care utilizations per month before and after the index-hospitalization where randomization occurred. For this analysis, the outcome for each individual is a count of urgent care utilizations. We will use a count regression with the dependent variable being the post-hospitalization count of urgent care, using the pre-hospitalization count as a covariate in the model. For this outcome, we will also construct a linear regression model using the mean change in the number of urgent care utilizations by randomization group. Finally, we will conduct an interrupted time series analysis using the times of the urgent care utilization, the randomization treatment group, a marker for pre versus post-index hospitalization. In this model, we will look for a significant difference in change in the slope of urgent care utilizations pre-post-index hospitalization by randomization group. We will evaluate sustained community tenure, (number of days out of 30 days that the Veteran is in their own home (as opposed to inpatient or in the emergency department). For this measure, we will first explore the distribution of the outcome to assess whether it fits best as a count distribution or a difference in mean proportion of days. We will then conduct a bivariate analysis with the dependent variable (sustained community tenure) and the independent variable (randomized group assignment).

Power Calculations:

For our primary outcome measure, we first estimated a mean number of urgent care visits (ED and hospitalization) for the six months pre-randomization and six months postrandomization for each patient. We know that readmission rates are between 12.7% and 21% annually for our Veterans, and ED visits will be similar or higher per year (thus urgent care use = 25%-40%). Thus, we estimate a monthly rate of urgent care use of 3% (40% annual/12 months) of our sample of 600 patients (thus a mean of 18 utilizations per month). Using a pre-intervention rate of 18 for both intervention and control, and a postcontrol change of 1, assuming an alpha of 0.05, and we have power (0.8) to detect a difference of differences in change in mean urgent care utilization of 0.75 with a standard deviation equal to the control mean.

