Our recruitment will occur over 24 months, post-discharge number of months of data will vary between six and twelve, and will extend back in time for up to 24 months, resulting in a total number of months between 24 and 36 for urgent care utilization. With these assumptions, we are powered to detect an effect size of 0.5 with an autocorrelation between 0.0 and 0.2.

Assuming a baseline rate of 1.0 and the mean exposure time to be 30 days, a sample of 300 patients in each group will achieve 80% power at a two-sided alpha level of 0.05 to detect a rate ratio of at least 1.0425. This calculation is based on a Poisson Regression with the number of 30-day sustained community tenure counts as the dependent variable and randomized group as a binary independent variable.

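### The primary urgent-care comparison is defined per month, but the count and linear models state no person-time term and no end of follow-up at death, and the pre- and post-index windows are not settled

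*Combined protocol and SAP*

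**What the plan says.** Section 3.5 (Analysis Plan) calls the primary effectiveness analysis a pre-post difference in differences, "comparing the number of urgent care utilizations per month before and after the index-hospitalization where randomization occurred". The outcome for each patient is then a count. The first model is given as: "We will use a count regression with the dependent variable being the post-hospitalization count of urgent care, using the pre-hospitalization count as a covariate". The second reads: "we will also construct a linear regression model using the mean change in the number of urgent care utilizations by randomization group". A third, an interrupted time series, works from the times of the events.

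The text on windows in the same section:

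- Analysis text: "For an 18-month period pre-index hospitalization and a six-to-twelve month period post-hospitalization (depending on time of" recruitment.
- Primary power text: mean urgent care visits "for the six months pre-randomization and six months postrandomization for each patient".
- Time-series power text: "post-discharge number of months of data will vary between six and twelve", and the data "will extend back in time for up to 24 months, resulting in a total number of months between 24 and 36".

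The Aim 3 hypothesis in section 1.0 gives no window. Section 3.4 lists date of death among the data to be obtained, but no analysis rule uses it. An exposure time is stated once, for the separate 30-day community tenure outcome: "Assuming a baseline rate of 1.0 and the mean exposure time to be 30 days".

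**The concern.** The stated quantity is a monthly rate, while the two regression sentences name a count and a change in number. Observation time differs between the pre and post periods. It also differs between patients, through recruitment date and through death. An analyst who follows the sentences as written would not produce a monthly rate.

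Three things are at stake. The linear result would have no clear meaning. The analysis would have no rule for patients who die, so an arm with more deaths could appear to use less urgent care. And with the windows unsettled, the primary result could be computed in more than one way after the data are seen.

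**Working it through.** **Exposure in the plan's own figures.** The community tenure calculation does use exposure time, and it reproduces. With log(1.0425) = 0.0416 and 30 days, N = (1.96 × 2 + 0.842 × sqrt(2 + 2/1.0425))² / (30 × 0.0416²) = about 600, as stated. The plan gives no corresponding calculation for the urgent-care models over unequal windows. Its primary power statement (a difference of 0.75) is a separate matter, and nothing below depends on it.

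**Windows.** A fixed 18-month pre period gives totals of 18 + 6 = 24 to 18 + 12 = 30 months. A fixed 24-month period gives 24 + 6 = 30 to 24 + 12 = 36. The stated 24 to 36 fits neither; it needs a pre period that varies from 18 to 24 months between patients.

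**Raw change with no effect.** At the plan's 3% per month: 0.03 × (6 - 18) = -0.36 and 0.03 × (12 - 18) = -0.18 uses per patient, in both arms. The monthly change is 0.

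**Power of the linear model.** From the documents: r = 0.03 per month, 300 per arm, 18 months pre, 6 to 12 post. Assumed: rate ratio 0.6, no deaths, post time t uniform on 6 to 12 (mean 9, variance 3, mean of 1/t = ln2/6), between-patient frailty variance f, two-sided alpha 0.05. The post rate q is 0.03 in control and 0.018 in Annie.

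- Variance of raw change = 18r + f(18r)² + 9q + f(9q)² + 3q²(1 + f) - 2f(18r)(9q). With f = 0.5 this is 0.8505 (control) and 0.7749 (Annie). The difference is 9 × 0.012 = 0.108, so z = 0.108 / sqrt(1.6254/300) = 1.467 and power is 31%.
- Variance of monthly change = (18r + f(18r)²)/324 + q ln2/6 + fq² - 2frq. This gives 0.005132 and 0.003818, so z = 0.012 / sqrt(0.008951/300) = 2.197 and power is 59%.
- For f from 0 to 1: 29 to 33% against 59 to 60%. At 25%/12 = 2.1% per month with f = 0.5: about 23% against 45%.
- Simulation with the pre-index count as a covariate, same settings at 3% per month: about 80% on either scale at f = 0, 77 to 78% at f = 0.5, and 74 to 76% at f = 1. Once pre use is adjusted for, it no longer matters that it was also subtracted.

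**Count model.** In simulation with f = 0.5, a true rate ratio of 0.6 and no deaths, power is 78.0% without the offset and 78.7% with it.

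**Death, no treatment effect.** The documents give no mortality rate. Assume 12-month mortality of 20% in one arm and 30% in the other, with exponential hazards -ln(0.8)/12 = 0.0186 and -ln(0.7)/12 = 0.0297 per month. Mean observed post time is then 8.26 and 7.86 months, and 7.86/8.26 = 0.95, which is the apparent rate ratio without an offset. Simulated rate ratios:

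| Assumed mortality | Without offset | With offset |
|---|---|---|
| 20% vs 30%, unrelated to use | 0.95 | 1.00 |
| 20% vs 30%, linked to use, f = 0.5 | 0.921 to 0.925 | 0.976 to 0.981 |
| 20% vs 30%, linked to use, f = 1 | 0.89 | 0.96 |
| 20% vs 25%, linked to use | 0.95 to 0.96 | 0.98 to 0.99 |
| Equal mortality | 1.00 | 1.00 |

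Smaller runs for the 20% vs 30% cases put the range at 0.89 to 0.96 without the offset and 0.96 to 1.01 with it. In the linked 20% vs 30% case, false rejection is 7 to 9% without the offset and about 5% with it.

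**The case against.** The comparison is introduced as per month, and the model sentences follow directly, so rates were probably intended. Silence about an offset is not a statement that none will be used. That is fair: the defect is an incomplete specification, not a declared choice of raw counts.

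A reader might go further in four ways that the documents do not support.

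- *Four conflicting primary windows.* Section 3.3b mentions urgent care use one month after hospitalization. That sentence concerns one-month follow-up data, fits the separate 30-day outcomes, and is not labelled as the primary window. The 6 and 6 months are how a power input was estimated, not a stated analysis window. What remains is 18 against up to 24 months pre, and a power basis that differs from the analysis.
- *A biased arm comparison.* Patients are randomized, so planned follow-up balances in expectation. The missing offset alone does not bias the contrast.
- *A primary analysis with halved power.* The 31% against 59% belongs to the additional linear model, and only if it is left unadjusted. No covariate is named for it, but none is excluded, and adjustment removes the gap.
- *Mortality that will distort the result.* This needs deaths to differ by arm, which in a coaching and texting trial is an assumption.

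The interrupted time series uses event times and is not criticized here.

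**Conclusion.** The point holds as a specification gap that should be closed before analysis. The omissions (no person-time term, no rule at death) and the conflict between 18 and up to 24 months are plain in the text and rest on no assumption. The -0.36 to -0.18 shift needs only the plan's 3% per month.

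The power figures depend on the assumed rate ratio of 0.6 and on there being no deaths. They show that baseline adjustment matters more for the linear model than the choice between raw and monthly scale. The death figures depend on assumed differential mortality. For the count model, the offset serves to give a monthly rate and to limit that one source of bias, not to gain power.

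**What to change.** - State one pre window and one post window, and use them in the analysis text and in both urgent-care power texts of section 3.5.
- Fit the count regression with a log(time alive and observed) offset that ends at death. If the pre window is allowed to vary between patients, enter pre-index use as a monthly rate.
- In the linear model, use the monthly rate adjusted for pre-index use, as the count model already adjusts.
- Report deaths by arm, and say that the offset reduces but does not remove bias if death is related to utilization.

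The cost is SAP wording and minor analysis work. Event dates and date of death are already requested, and no new patient contact is needed. The rate while alive must be named as the estimand, since it is a choice and not merely a correction.

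The choice of window has its own trade-off. Six and six months is available for every planned follow-up but is less powerful than 18 and 6 to 12. For the count regression with offset, power is 62% against 78% (rate ratio 0.6, frailty variance 0.5 and no deaths assumed).
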